#### **9.3.1 Subject Safety**

Study eligibility is confirmed by study coordinators. Breast Clinic physicians and Breast Surgeons will receive information when this study is activated through presentations by the study PI. The study coordinator will review medical records of patient with a diagnosis of ADH, ALH, LCIS, and/or increased breast cancer risk to confirm that they meet eligibility criteria. The patient's physician will be notified by the study coordinator of the intent to approach the patient for inclusion in this study.

There are no safety tests/questionnaires.

The patients will be informed that they are to contact the study coordinator if they encounter any problems with their treatment. The study coordinators will update the BBD study team of any anticipated adverse event at team meetings every other week ([name] and [name] group will send an e-mail to the coordinator team at [[contact]](mailto:[contact]) who will bring this to the regular meeting and get back to [name] or [name] team that the side effect was reviewed). If a serious adverse effect occurs, the study coordinator will contact the PI (Drs.

[name], [name] or [name]), or her designee when PI is away from the clinical setting ([name], [name], [name]). Serious Adverse Events and contact processes are covered under 10.2.

### **9.3.2 Data Integrity**

Data regarding study start and consent will be kept in PTRAX at Mayo. Northwestern University and MD Anderson Cancer Center at Cooper will follow their institution's tracking system. The following data will be recorded in the study database (RAVE) by the study coordinators:

- Study sample attainment dates
- Drug start and stop dates
- Deviation(s) from the prescribed dosage regimen will be recorded.
- Missed drug dates or deviations for the prescribed dosage regimen reported by the patient will be reviewed with participant and documented in the study database. Participant diaries will be retained in the subject folder as source documents.
- Attribution to the study agent
- Adverse effects assessed according to CTAE terminology, along with start and stop dates; CTAE severity score (AEs without a CTCAE term will be graded according to general severity guidelines)
- SAEs, date and level, whether codes were broken to identify agent
- BCPT symptom survey results

### **9.3.3 Product Accountability**

- The research pharmacy will store the drug kits in their area at each institution.
- When a patient has agreed to participate in the study, they will be randomized per the RAVE Medidata database. Once randomized, the research pharmacy will be notified of randomization results and will prepare kit for dispensing when the order and communication form is received from the study coordinators. The pharmacist will then dispense the kit to the study coordinator, who will deliver it to the patient, and provide instructions to the patient.
- The research pharmacy will be accountable for the drug kits.

### **9.3.4 Study Documentation**

Study coordinators will maintain subject files. They are responsible for keeping these files up to date.

### **9.3.5 Study Coordinator**

The BBD group works as a team and has study coordinators available to support the study. Funding for this study coordinator support is provided by the parent R01 grant funding the study. Team meetings will be held every other week. We will have monthly communications with [name] at Northwestern University and [name] at MD Anderson Cancer Center at Cooper. A SAE will stimulate an immediate meeting with [name] and the DSMB.

## **9.4 Breaking Codes in Double-Blinded Studies**

A) **Situations requiring codes to be broken:** There are three distinct situations in which it is appropriate to break the codes for individual patients

enrolled in double-blind trials:

- (1) In the event of an emergency or a serious adverse event for an individual patient.
- (2) In the event that it would be helpful for the future clinical care of an individual patient after she/he has completed participation in the trial.
- (3) When it is necessary to know the specific treatment assignment of each patient in the trial in order to manage them all appropriately after they have completed participation in the trial.

Study participants will receive study medications, blinded, from the investigational pharmacy. The blind will be maintained through the effort of the research pharmacist and the pharmacy.

In the event of an emergency or a serious adverse event, the PI (or their designee) will be notified to assess the medical necessity of unblinding. Emergency unblinding should only occur in medical events where not knowing the treatment assignment will affect ongoing treatment or significantly compromise the clinical management of the patient.

Unblinding due to a Serious and Unexpected Adverse Event will happen only with permission of [name], or designated site PI in the event of emergency if [name] cannot be reached.

Breaking the blind for serious and unexpected adverse events could occur when:

1. The blind should be broken for serious and unexpected adverse events that would meet the criteria for reporting as single occurrences or one or more occurrences. The blind would need to be broken to determine if there is a reasonable possibility that the drug caused the adverse event.
2. If the blind is broken and the subject was receiving **placebo**, the event should not be reported in an IND safety report because there is not a reasonable possibility that the study drug caused the adverse event.
3. If the blind is broken and the subject was receiving **drug treatment**, the suspected adverse reaction must be reported in an IND safety report. (Note: the case must meet the definitions of suspected adverse reaction, serious, and unexpected.)

If unblinding is necessary and after PI approval, the Mayo Clinic team designee will contact the site-specific pharmacy or statistical team / data manager to break the code while protecting the PI from the unblinded information, unless unblinding the PI is deemed necessary for either patient management or required event reporting. The reason and date of unblinding should be documented in Medidata RAVE by the statistical team / data manager.

**Northwestern University Pharmacy:**

**[contact]**

**Email: [[contact]](mailto:[contact])**

**MD Anderson Cancer Center at Cooper Pharmacy:**

[contact]

Email: [[contact]](mailto:[contact])

If, in the judgment of the attending physician, it would be helpful for the future clinical care of the individual patient, the code may be broken if requested by the patient, and *after* the patient has discontinued any duration of the study drug interventions, and no sooner than one month AFTER discontinuation of the study drug interventions while protecting the PI from the unblinded information. That is, after the patient has been fully evaluated and all evaluation information has been recorded by the attending physician and the patient (if appropriate), the patient's clinical care team (but not the study PI) may request information on which study therapy the patient was receiving and share this information with the patient. Information on the assigned treatment arm may be obtained per preferred institutional process, either via the Research Pharmacy or via a designated study team member other than the PI (Mayo Clinic).

#### **9.5 Ancillary Treatment/Supportive Care**

The duration of the intervention is short; thus, short-term toxicity is expected to be limited to only temporary vasomotor symptoms.

#### **9.6 Dose Discontinuation Criteria**

Any subject with an adverse event Grade 3 or higher (unless judged to be definitely unrelated to study agents) will be discontinued from both oral and topical interventions. These subjects may choose either to proceed with post-intervention blood and tissue samples, to continue participation with only clinical and symptom survey follow-up, or to withdraw from all further participation in the study.

#### **9.7 Full Supportive Care**

Patients should receive full supportive care while on this study. This includes blood product support, antibiotic treatment, and treatment of other newly diagnosed or concurrent medical conditions.

#### **9.8 Definitions**

##### *Protocol Deviations*

Noncompliance with the research protocol that does not increase risk or decrease benefit and/or affect the integrity of the data

##### *Protocol Violation*

Noncompliance with the IRB-approved protocol without prior sponsor and IRB approval. Violations generally increase risk or decrease benefit, affect the subject's rights, safety, or wellbeing, or impact the integrity of the data

##### *Noncompliance*

Defined as a failure to follow the regulations, applicable law, institutional policy, and deliberations of the IRB

##### *Adverse Event*

Any unfavorable symptom, sign, or disease (including an abnormal laboratory

finding) temporally associated with the use of a medical treatment or procedure, whether or not considered drug related.

*Suspected Adverse Reaction*

Any adverse event for which there is a reasonable possibility that the drug caused the adverse event.

*Expedited Reporting*

Expedited Reporting Requirements for IND/IDE Agents

Late Phase 2 and Phase 3 Studies: Expedited Reporting Requirements for Adverse Events that Occur on Studies under an IND/IDE within 30 Days of the Last Administration of the Investigational Agent/Intervention *Routine Reporting* Events reported to sponsor via case report forms

*Events of Interest*

Events that would not typically be considered to meet the criteria for expedited reporting, but that for a specific protocol are being reported via expedited means in order to facilitate the review of safety data (may be requested by the FDA or the sponsor).

**9.9 Adverse Event Characteristics**

Adverse events will be collected starting at the On Study visit and ending 30 days after the post-treatment biopsy is completed. Each participant will be asked about AEs at every study visit and participant contact. AEs will be documented and logged in the RAVE Database.

CTCAE term (AE description) and grade: The descriptions and grading scales found in the revised NCI Common Terminology Criteria for Adverse Events (CTCAE) version 5.0 will be utilized for AE reporting. All appropriate treatment areas should have access to a copy of the CTCAE version 5.0. A copy of the CTCAE version 5.0 can be downloaded from the CTEP web site: <https://prevention.cancer.gov/clinical-trials/clinical-trials-management/cp-ctnet-instructions-forms>

- a. Identify the grade and severity of the event using the CTCAE version 5.0.
- b. Determine whether the event is expected or unexpected (see Section 6.11).
- c. Determine if the adverse event is related to the study intervention (agent, treatment, or procedure).
- d. Determine whether the event must be reported as an expedited report. If yes, determine the timeframe/mechanism (see Section 10.3)
- e. Determine if other reporting is required (see Section 10.0-10.2)
- f. Note: All AEs reported via expedited mechanisms must also be reported via the routine data reporting mechanisms defined by the protocol.

Note: A severe AE is NOT the same as a serious AE, which is defined in Section 10.2

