#### 5.0 Test Schedule

Test & Procedures	Baseline	End of Treatment (at the end of 4 weeks of treatment) 
Pregnancy Test (serum or urine)	X 	
Follicle stimulating hormone (FSH)	X 	
Baseline labs [CBC and Liver Function testing (ALP, ALT, AST, ALB, TP, BILI), creatinine coagulation labs (fibrinogen, Antithrombin 3)]	X 	X 
Physical Examination	X 	X 
Two 10 ml amounts of blood (will be stored for future research)	X 	X 
Blood Draw (4-OHT bioavailability)		X 
Research Biopsy of Breast Tissue - same quadrant as diagnostic biopsy  [Ki67, NanoString, 4-OHT bioavailability (post-treatment only);] Pretreatment diagnostic biopsy is OPTIONAL if meets requirements	X 	X 
Digital Screening Mammogram	X 	X 
MBI (Mayo Clinic site only)	X 	X 
BCPT Symptom Survey	X 	X 
Symptom /safety/AE assessment	X 	X 

1. For women of childbearing potential only.
2. Research Funded (Note: clinical surgical consult will not be research funded.)
3. For women with unknown menopausal status
4. Physical exam could be done within 3 months before treatment starts.

5. Blood for storage two 10 ml blood draws using purple top EDTA tubes – protect from light exposure (i.e., wrap in tin foil, use light sensitive brown bags). **First EDTA tube**- Aliquot (1) 4000uL blood pour for DNA extraction. Refrigerate, Centrifuge at lab standards. Process for three 1 ml aliquots of plasma into 3 cryovials 1 ml plasma each and 1ml WBC. Light Sensitive. Store in -80 freezer. **Second EDTA vial** is stored as whole blood.
6. Blood for 4-OHT bioavailability. 4 ml. green top heparin tube. Process for plasma. Protect from light exposure as light sensitive (i.e., wrap in tin foil, use light sensitive brown bags). Store in -80 freezer.
7. Baseline Pretreatment research tissue core biopsy information is located in Appendix F.

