## **7.2 Participant Contact**

Participants will be contacted 1 week (+/- 2 days) after study drug initiation. A phone call, portal message, or email at Week 1 will be to assess compliance, toxicity, and changes in medication and to address any questions by the participant.

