### **8.0 Study Conduct**

Mayo Clinic IRB approval of the protocol and any amendments will be required prior to implementation. Subject records will be stored in a secure location and subject confidentiality will be maintained. The investigator will be thoroughly familiar with the appropriate use of the study drug as described in the protocol. Master files of essential clinical documents will be maintained for the duration of the study.

During the patient's clinical visit to discuss findings of AH, LCIS, or increased breast cancer risk, the patient's physician will introduce the study to the patient. If the patient

agrees to participate in the study, a study coordinator will answer any additional study questions and start the informed consent process. The study coordinator will also provide, as indicated, appointments for a pregnancy test and FSH levels, baseline labs along with all other pre-treatment tests and procedures. The patient will be given a study kit by the RN study coordinator with directions for taking the pills and applying the gel. The study coordinator will also schedule a return visit appointment, in which the patient will complete the BCPT symptom questionnaire, along with post-treatment blood tests, study mammogram, breast biopsy (core or excisional), and study MBI (only at Mayo clinic) at the completion of treatment. Post-study breast biopsy and blood draw must be scheduled between days 25-31 of drug treatment with the last dose of study drug within 2 days (preferably within 24 hours) prior to the post-treatment biopsy and blood draw.

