Other post-treatment tests will be scheduled PRIOR to the breast biopsy but not more than 3 days prior to the post-treatment breast biopsy. The RN coordinator will instruct patient that they need to avoid pregnancy during this treatment and 2 months after treatment and instruct: The effects of topical 4-OHT gel on the developing human fetus at the recommended therapeutic dose are unknown. However, oral tamoxifen is Pregnancy Category D—Positive evidence of human fetal risk. For this reason, and because triphenylethylene antiestrogens, including tamoxifen, are known to be teratogenic, women of childbearing potential and their male partners must agree to use at least one effective form of birth control (abstinence is not an allowed method) prior to study entry and for the duration of study participation, and for two months following the last dose of study medications (participant can resume oral birth control pills for effective birth control measures after post-treatment biopsy is done). Effective birth control methods are copper and Mirena IUD (intrauterine device), diaphragm/cervical cap/shield, spermicide, contraceptive sponge, condoms; these may be used during and after treatment. Oral contraceptives may only be used after the 4-week treatment is complete, and the post-treatment biopsy is obtained. Women of childbearing potential must have a negative pregnancy test (either serum or urine pregnancy test) within five days before starting study medications. Tubal Ligation is also an acceptable form of birth control. Should a woman become pregnant or suspect she is pregnant while participating in this study, she should inform her study physician immediately.

If DCIS or invasive cancer is identified by the breast pathologist during the clinical read of the research biopsy H&E, then this information will be relayed to the assigned clinical care provider (surgeon if upcoming surgery or Breast Clinic physician if no surgery is planned).

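### AE collection runs to 30 days after the post-treatment biopsy, but no visit or contact is scheduled in those 30 days at which to ask about AEs

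*Combined protocol and SAP*

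**What the plan says.** Section 9.9 defines both the window and the method. The window: "Adverse events will be collected starting at the On Study visit and ending 30 days after the post-treatment biopsy is completed". The method: "Each participant will be asked about AEs at every study visit and participant contact".

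The occasions for asking are set elsewhere:

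- **Section 5.0** has two columns, Baseline and End of Treatment. The row "Symptom /safety/AE assessment" is marked in those two and nowhere else.
- **Section 7.2** adds one contact, by phone, portal or email: "Participants will be contacted 1 week (+/- 2 days) after study drug initiation". Its stated purposes include assessing toxicity.
- **Section 8.0** fixes the end of the schedule: "Post-study breast biopsy and blood draw must be scheduled between days 25-31 of drug treatment". Study drug is to be stopped no more than 2 days ahead of these procedures. It also says: "Other post-treatment tests will be scheduled PRIOR to the breast biopsy but not more than 3 days prior".
- **Section 9.2** requires a return to the consenting institution at the end of treatment and names no later return.

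Two reporting rules cover the same period. Section 10.3 sets expedited reporting for events within 30 days of the last administration. Section 10.2 requires reporting of any death within 30 days of the last treatment or procedure. Section 11.0 puts every patient who started treatment into the AE analysis.

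**The concern.** The method of collection has nothing to attach to in the last part of the window. If AEs are asked about at visits and contacts, and none follows the biopsy, a site that follows the protocol exactly will record only what women choose to report during those 30 days.

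Three things are at stake:

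- The post-treatment tissue sample is mandatory, and complications of taking it can arise only once it has been taken, which is when scheduled questioning stops.
- The 30-day post-dose period on which expedited reporting depends falls almost wholly in the same gap.
- Events up to the biopsy come from active enquiry and events after it from volunteered reports. Section 11.0 does not separate the two, so a low count after the biopsy could reflect few events or few questions. This matters more because the gel dose was raised to 8 mg/day during the trial, and section 2.0 reports a pulmonary embolism judged possibly related at that dose.

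**Working it through.** The plan states no figure on this point to reproduce. The check sets the window against every scheduled occasion and then works out the timing.

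**1. Scheduled occasions**

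| Occasion | Section | Timing | After the biopsy? |
|---|---|---|---|
| Baseline assessment | 5.0 | Before first dose | No |
| Week-1 contact | 7.2 | 1 week ± 2 days after start | No |
| Mammogram, MBI | 5.0, 8.0 | Up to 3 days before biopsy | No |
| End-of-treatment visit, survey, biopsy, blood | 5.0, 8.0, 9.2 | Biopsy on days 25–31 | No |
| Patient diary | Appendix E | Daily dosing and symptoms, brought to the follow-up visit | No |

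Scheduled AE enquiries after the biopsy: 0.

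**2. Other provisions that might fill the gap**

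- Section 9.3.1: participants are told to contact the coordinator about problems with their treatment. This is volunteered, and its wording does not clearly cover a biopsy complication after treatment has ended.
- Section 9.6: women discontinued for a Grade 3 or higher AE may choose clinical and symptom-survey follow-up. No timing is given.
- Section 13.3: women who withdraw are offered follow-up for AE resolution, as clinically needed.
- Section 9.4: a code break at least one month after stopping drug happens only on request.

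All are passive or conditional. None is a scheduled enquiry for a woman who completes the study.

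**3. Share of the period from first dose**

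End of collection = biopsy day + 30. Uncovered share = 30 / (biopsy day + 30).

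- Biopsy on day 25: end on day 55; 30/55 = 54.5%.
- Biopsy on day 28: end on day 58; 30/58 = 51.7%.
- Biopsy on day 31: end on day 61; 30/61 = 49.2%.

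**4. Share from the On Study visit**

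Collection starts at that visit, and the documents do not give the gap L between it and first dose. Share = 30 / (L + biopsy day + 30). Section 6.7 allows imaging and research biopsy up to 7 days, and examination and labs up to three months, before treatment starts. As illustrations:

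- L = 7 days: 30/68 = 44.1% to 30/62 = 48.4%.
- L = 90 days (assumed for three months): 30/151 = 19.9% to 30/145 = 20.7%.

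The share falls only because the pre-treatment period lengthens. The uncovered stretch stays at 30 days.

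**5. Overlap with the expedited-reporting period**

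The last dose is d = 0 to 2 days before the biopsy, so the 30 days after it end 30 − d = 28 to 30 days after the biopsy. The part lying after the biopsy is 28/30 = 93% to 30/30 = 100%.

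**6. Women who could still be reached**

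The accrual target is 104. Section 2.0 says 10 had finished intervention and study procedures by 10/12/2022, so at most 104 − 10 = 94 could receive a new contact. The number remaining now is not given.

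**The case against.** The strongest reply is that the window is not empty. Section 9.9 does not limit asking to scheduled contacts. Women can call the coordinator, and the team reviews AEs every other week (9.3.1). Biopsy slides are read within 21 days, and DCIS or cancer is passed to the care provider. SAE and death reporting extends to 30 days and beyond. Serious events are arguably the ones most likely to be volunteered. This stands in part: a reader might infer that AEs after the biopsy go uncollected, and the documents do not support that. They show only that no one is scheduled to ask.

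A reader might also infer that AE comparisons between arms would be distorted, or that tables would present volunteered reports as complete. Neither is supported. Section 11.0 defines the AE analysis set but no table layout or arm comparison. The trial is double-blind with the same follow-up in each arm, so under-recording would be expected to be broadly similar across arms. That does not remove the problem, since similar under-recording still lowers the count in every arm.

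Two limits also stand. A share of days is not a share of risk, and sections 9.5 and 11.0 expect short-term toxicity to be limited to temporary vasomotor symptoms. AEs are not a listed aim in section 3.0, so the Ki67 endpoint is untouched.

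Finally, the schema figure is not shown, and the End of Treatment column carries a note 12 with no item of that number in the text as read. The unnumbered text after item 11 is probably that note, and it deals only with scheduling end-of-treatment tests. Sections 7.2, 8.0 and 9.2 describe the contacts independently, and none follows the biopsy.

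**Conclusion.** The mismatch is real and should be put right. Section 9.9 declares a 30-day post-biopsy window, and the rest of the protocol schedules no enquiry in it. Followed as written, the plan leaves that window to volunteered or conditional reports, including for complications of a mandatory procedure and for 93% to 100% of the 30-day post-dose reporting period.

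The 30 days are about 49% to 55% of the period from first dose to the end of collection, and a smaller share from the On Study visit, depending on a gap the documents do not state. These figures apply to women who have the biopsy on days 25 to 31, and they assume that the missing figure and note contain no further contact.

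How many events would be missed cannot be estimated, because no spontaneous-reporting rate is given. The point concerns completeness of safety data. It shows no bias between arms and no effect on the primary analysis.

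**What to change.** Add to sections 5.0 and 7.2 one AE contact by phone, portal or email, in the week-1 format, for all women still to complete the study. Place it on or shortly after day 30 post-biopsy, for example on days 30 to 35, and ask about the full 30 days. A symmetric allowance such as ± 3 days would let the contact fall on day 27 and leave up to 3 days of the window unasked.

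In the AE analysis, tabulate post-biopsy events separately for women who completed before the contact was added, because theirs are spontaneous reports only.

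If the contact is not adopted, the least that is needed is for section 9.9 to say that the post-biopsy window relies on spontaneous reports, and for those events to be shown separately for everyone.

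The cost is a small amendment and one short coordinator contact per remaining participant, at most 94 on the 10/12/2022 figures. It needs no new procedure and does not touch dosing, treatment or discontinuation rules.
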